## Aim 3: Qualitative Interviews for Process Evaluation

A random subset of approximately n=27-40 intervention participants (4-16 from each site) will complete key informant interviews at the conclusion of the intervention. Participation in these interviews will be voluntary and discussed when they provide informed consent to the intervention (aim 2). Veterans will be paid \$20 for completion of interview. In addition to collecting information from Veteran participants, we will also reach out to clinicians at all 4 sites who interacted with the intervention program/staff. These will likely be ID clinicians, and

we will collect feedback related to their thoughts on the intervention delivery and future sustainability/implementation. Feedback will be collected via VA-approved methods as written or oral questions, based on clinician's preference and availability (VA encrypted email, VA REDCap survey, Microsoft Teams, and/or telephone calls). Providers/staff will not be compensated.

For the Veteran participants who complete interviews, they may also be contacted 6-12 months after completing the intervention for a second brief interview. The purpose of these interviews to hear participants' long-term perspectives from completing the study and developing a better understanding of the sustainability of the intervention.

## Risk

This study is enrolling Veterans living with HIV. While this group is considered a vulnerable population, the study team has considerable experience enrolling these participants and adapting interventions that are culturally sensitive. Given the increased prevalence of ASCVD risk factors among Veterans with HIV, it is important that they are not excluded from participation in this study. We will use VA CDW to identify the initial patient sample using the inclusion/exclusion criteria. Each site's respective electronic medical record system (CPRS) will be used for a second screening level for information not readily available as normalized data in VA CDW prior to contacting patients. If investigators identify any SAE outcomes of interim findings which have the potential of affecting participants' health or welfare, the veterans as well as their PCP will be notified using secure VA notification processes.

### Potential risks

- a. ***Loss of confidentiality.*** The risks associated with gathering mixed methods data from participants by properly trained and supervised research assistants and technical staff is low and include risks of loss of privacy and psychological distress associated with asking questions relevant to a sensitive diagnosis like HIV.
- b. ***Detection of clinically significant problems:*** Although not caused by study participation, it is possible that clinically significant problems will be detected by study staff. Subjects entering the study will have a history of hypertension so we expect to see abnormal systolic and diastolic values. All values that reach a safety threshold (<90 or >180 systolic BP, <40 or >110 diastolic BP) will be reported to the subjects' care provider as soon as possible.
- c. ***Kidney disease and electrolyte imbalances:*** Some of the blood pressure agents used in the interventionist-managed protocols may cause acute kidney injury and electrolyte imbalances. Subjects with underlying kidney disease at baseline will be at higher risk.
- d. ***Drug-drug and Drug-disease interactions for ART treatment.*** Each site will have a clinical site leader who is an infectious disease doctor familiar with current CVD/HIV treatments to ensure that there are no drug-drug interactions.
- e. ***Other medication side effects:*** All medications have potential side effects. Medications used in the interventionist managed protocols will only be recommended by the interventionist and must ultimately be prescribed by the subject's treating provider according to his/her best clinical judgement and approval. Common side effects of anti-hypertensive medication include but are not limited to: bradycardia, lightheadedness and orthostatic hypotension, lower extremity edema, kidney injury and electrolyte imbalances (see above), and myalgias.
- f. ***Physical activity.*** All subjects will be encouraged to increase their physical activity, raising the possibility of musculoskeletal injury or unmasking of ischemic heart disease. Risks from increased physical activity will be minimized by encouraging moderate rather than vigorous activity. Providers will respond to these patient problems per usual medical practice.
- g. ***Smoking and Alcohol Misuse.*** All subjects will be encouraged to quit smoking (if currently using), raising the possibility of withdrawal symptoms from nicotine dependence. Participants will also be screened for alcohol misuse.
- h. ***Psychological risks.*** We do not anticipate any substantial psychological risks to be associated with participation in this study. As part of our assessments, we will ask participants about their demographic characteristics (i.e., race/ethnicity, socioeconomic status). It is possible that some participants may feel

uncomfortable answering some of these questions. We will only ask questions that involve data that are important for study outcomes, and we will inform patients that they may refuse to answer any interview or survey questions, but still be involved in the study. It is also possible that participants may be uncomfortable talking with the Prevention Interventionist about some topics that are included in patient-based intervention. We have not experienced any significant issues regarding this in our prior qualitative or mixed-methods studies with Veterans who are HIV+. However, subjects will be permitted to skip any topics that make them feel uncomfortable, and subjects will be informed that if they choose to discontinue the study at any time, this will not interfere with their usual medical care.

**Adequacy of Protection Against Risks.** The specific risk of participation are noted above; procedures for protection follow.

- a. **Protection of participants' identities and confidentiality:** Because this study involves persons with HIV, steps must be taken to protect not only the data they provide, but also their identities. The following confidentiality-protection steps will be taken: [1] All research staff will participate in initial training, follow-up training, and ongoing monitoring and supervision to ensure their understanding of ethical issues involved in this research; [2] consent forms will be maintained in locked files with limited access, separate from any subject data and will only be accessible to the study team; and [3] any personal identifiers linked to data will be removed and replaced by code numbers in all records. These steps are not foolproof, and participants will be informed of the associated risks at the time of informed consent. Research staff will spend approximately 20 hours in initial training sessions and observed practice. Training includes reading and discussing research protocols and selected articles about interviewing, tracking, vulnerable participants and attending lecture sessions regarding emergency procedures, mandatory reporting, confidentiality, and research ethics. Training also will include how to handle transient discomfort or distress related to embarrassing or sensitive discussions as well as how to identify and respond to signs of acute distress; experienced staff will be available for immediate consultation in the event of unexpected acute psychological problems; and all staff will be made familiar with referral resources and procedures for psychological, social service, substance-use treatment, and other emergency needs. When appropriate, material specific to interacting with persons living HIV and the sensitivity of the diagnosis will be provided to research staff as part of their training curriculum.
- b. **Blood Pressure:** All participants will have a high risk for CVD, and thus many will be prescribed hypertension medications by their health care provider at the outset of the study. It is likely that as a result of increased monitoring, we will detect more episodes of abnormal BP values. Because of potential high and low BP values, subjects in the intervention arm may have their current hypertension regimen adjusted, subjects in the education control are will be asked to contact their provider for follow-up. [We will proactively address BPs for participants in the control group. If BP is identified by study staff as being high ( $>180/110$ ), similar to prior trials), we will provide feedback to both the patient and their provider via developed CPRS template and/or phone calls. If no action is taken, the study physician at each respective site will follow up with the patients' provider.] Safety monitoring of BP will occur in the context of home BP monitoring as well as BP measurement during data collection visits. An average SBP at any study visit or during home blood pressure monitoring  $> 180$  mm Hg and/or diastolic is  $> 110$  mm Hg will be considered an alert value and will trigger assessment by the clinician. Furthermore, an average at any study visit or during a home blood pressure monitoring that is  $< 90$  systolic or  $< 40$  diastolic would also be considered an alert value and would trigger an assessment by a clinician. Participants who have an alert reading at home will be asked to contact the clinician directly so that she/he can assess for any cardiovascular symptoms.

Participants who have an alert BP reading during study visits will be directly assessed for cardiovascular symptoms. Once an alert value has been confirmed, the participant will be triaged according to follow-up recommendations from Joint National Committee Recommendations (JNC 8). Participants will have access to their regular providers as well as the following study clinician investigators designated as the clinical contact for each site:.. If at any time, participants have symptoms of acute end organ damage (i.e. current chest pain, dyspnea at rest, new onset of blurry vision, or new neurological deficits consistent with a stroke) in the context of an elevated BP measurement (SBP

>180, and/or DBP >110), participants will be asked to contact their clinician and will be advised and assisted in seeking emergency medical care. For participants in the intervention group whose average SBP >180 and DBP >110 or SBP < 90 or DBP < 40 but are without acute symptoms, the participant's healthcare provider will be notified and medications will be changed as deemed appropriate by the study team. Follow up contact with the study staff will occur within one week. All abnormal blood pressure results will be communicated to the clinic director at each site who will be an integral part of triage and ensuring follow up. Any change in medication management or observation of an alert value will be communicated from the interventionist as soon as possible. The prevention interventionist will then generate a note to be entered into the electronic medical record and will communicate directly with the subject's PCP. To facilitate the efficiency of this alert mechanism, the prevention interventionists will be encouraged to familiarize themselves with relevant clinic providers and staff and integrate themselves into the clinic workflow as completely as possible.

- c. **Lifestyle Interventions (Smoking Cessation, Alcohol Misuse, Physical Inactivity):** The interventionist will explore potential barriers to meeting recommended levels of exercise using motivational interviewing techniques as well as setting goals for exercise. The interventionist will screen for alcohol misuse using SBIRT for Veterans who screen positive for alcohol use and make referrals to the Primary Care-Mental Health Integration (PC-MHI) program where Veterans with alcohol misuse are more likely to receive care. Screening, brief intervention, and referral to treatment (SBIRT) is an integral part of nursing practice. The interventionist will screen for tobacco cessation (smoking, smokeless, e-cig, vaping). Barriers to initiating and maintaining smoking cessation will be explored and benefits emphasized. Among those in the process of quitting smoking or recently stopped, strategies to maintain smoking cessation will be explored. The interventionist explored potential barriers to smoking cessation using motivational interviewing techniques and setting goals for smoking cessation. The interventionist will provide a direct referral to the smoking cessation clinic and ensure that the study physician puts in a prescription for NRI when appropriate. Additionally, the interventionist will provide resources related to these behaviors and when appropriate, refer individuals for follow-up care.
- d. **Medication adverse effects, including kidney and electrolyte imbalances:** All participants who are prescribed a clinically indicated new medication according the interventionist-managed protocol will have that medication prescribed by the participant's usual health care provider, who will take primary responsibility for counseling the patient about side-effects and ordering follow-up laboratories. In addition, each participant will be counseled by the prevention interventionist about possible side effects and need for any monitoring. These protocols therefore will provide an additional level of monitoring compared to routine clinical care. Anti-hypertensive medication: Any patient prescribed an ACE-inhibitor, angiotensin receptor blocker, diuretic, or aldosterone antagonist, will be asked to return in 7-10 days for a repeat chemistry panel to check kidney function and electrolytes. The blood pressure algorithm will have special recommendations for those with more advanced chronic kidney disease (eGFR <60). Providers caring for study participants with conditions including but not limited to CKD and ASCVD, will be permitted to take their patients off of any protocolized management. Providers will take primary responsibility for the prescription of any medications in this study.
- e. **Drug-Drug and Drug-disease interactions with ART.** Each site will have a clinical site leader who is an infectious disease doctor familiar with current CVD/HIV treatments to reduce any potential drug-drug interactions. Our three CVD/ID specialist and ID site specialist will provide input on antihypertensive choice before initiation. If the patient's ASCVD risk estimate is  $\geq 5\%$  over 10 years, based on current guidelines it is reasonable to begin moderate-intensity statin therapy. Antiretroviral therapy may adversely affect lipid levels, glycemic control, and endothelial function and has been associated with adverse changes in body composition (lipodystrophy). However, use of newer agents may lessen the metabolic derangements of antiretroviral therapy.

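### The high-BP alert step for asymptomatic intervention participants requires SBP >180 and DBP >110 together, although the protocol's own alert definition needs only one of them

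*Protocol*

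**What the plan says.** All the relevant text is in Protocol Section 5.1.

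- **Potential risks, item b (detection of clinically significant problems).** Each limit counts separately: "All values that reach a safety threshold (<90 or >180 systolic BP, <40 or >110 diastolic BP) will be reported" to the care provider.
- **Adequacy of Protection Against Risks, item b (Blood Pressure), alert definition.** The average systolic limit of 180 and the diastolic limit of 110 are linked by "mm Hg and/or diastolic is", so either one makes an alert and prompts clinician assessment. It continues: "Once an alert value has been confirmed, the participant will be triaged according to follow-up recommendations" of JNC 8.
- **Same item, participants with symptoms of acute end-organ damage.** The trigger is SBP ">180, and/or DBP >110), participants will be asked to contact their clinician" and are helped to seek emergency care.
- **Same item, intervention participants without symptoms.** The step covers those "whose average SBP >180 and DBP >110 or SBP < 90 or DBP < 40 but are without acute symptoms". Their provider is notified and the study team changes medication as it judges appropriate. The next sentence reads "Follow up contact with the study staff will occur within one week" and carries no trigger of its own.
- **Same item, general provisions.** "All abnormal blood pressure results will be communicated to the clinic director at each site", who is part of triage and of ensuring follow-up. Also, "Any change in medication management or observation of an alert value will be communicated from the interventionist as soon as possible".

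**The concern.** Three statements of the high threshold treat either limit as sufficient. The fourth, which sets the action for asymptomatic intervention participants, requires both. It cannot comfortably be read as meaning either limit, because the same sentence uses 'or' for the low limits and the sentence before it uses 'and/or'.

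What is at stake is the alert-triggered medication step and the one-week contact. One week is the only participant follow-up interval that the protocol itself states for an asymptomatic BP alert. Without it, a participant with one high limit crossed falls back on the two-weekly call for poor BP control, unless the JNC 8 triage or the clinic director arranges something sooner. The documents do not show whether that triage sets an interval. This is also the arm in which drug treatment is being intensified.

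**Working it through.** **1. Trigger logic.** Apply each rule to an asymptomatic intervention participant.

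| Average BP | Alert by definition (either limit) | Reportable to provider (any limit) | Meets the asymptomatic step as written |
|---|---|---|---|
| 190/95 | yes | yes | no |
| 172/114 | yes | yes | no |
| 190/115 | yes | yes | yes |
| 88/60 | yes | yes | yes |

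Only high readings that cross a single limit fall through. Low readings do not.

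**2. How often this would happen.** The plan gives no figure to reproduce, so this is an illustration.

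Inputs from the documents:
- SBP SD 17 and baseline mean 145 (Section 5.6, Power).
- Intervention mean at 12 months under the hypothesis: 145 - 1 - 6 = 138. Using 145 throughout is the no-change case.
- Missing visits of 5%, 10% and 15% at 4, 8 and 12 months (Section 5.6, Power). With 150 per arm, expected intervention follow-up visits are 150 x (0.95 + 0.90 + 0.85) = 405.

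Inputs assumed, because the documents give no diastolic figures: DBP mean 80, 85 or 90; SD 10, 11 or 12; correlation with SBP 0.5, 0.6 or 0.7; bivariate normal.

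Formulas:
- P(either) = P(S>180) + P(D>110) - P(both)
- Single-limit share = 1 - P(both)/P(either)
- Single-limit visits = 405 x [P(either) - P(both)]

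Mid case (SBP mean 145, DBP mean 85, SD 11, correlation 0.6):
- P(S>180): z = (180 - 145)/17 = 2.06, giving 0.0198
- P(D>110): z = (110 - 85)/11 = 2.27, giving 0.0115
- P(both) = 0.0032
- P(either) = 0.0198 + 0.0115 - 0.0032 = 0.0281
- Single-limit share = 0.887; visits = 10.1 (from unrounded probabilities)

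With SBP mean 138 and the same diastolic inputs, the share is 0.906 and the count 6.1 visits.

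Full grid:

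| SBP mean | Single-limit share of high alerts | Single-limit visits of 405 |
|---|---|---|
| 138 | 0.86-0.97 | 2.8-20.0 |
| 145 | 0.81-0.98 | 7.9-22.5 |

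The minimum count is at SBP 138, DBP mean 80, SD 10, correlation 0.7. The maximum is at SBP 145, DBP mean 90, SD 12, correlation 0.5, where P(either) = 0.0616 and P(both) = 0.0060. Visits crossing both limits number 0.1 to 4.1 over the whole grid.

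**3. What the other safeguards supply for a single-limit high alert.**

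| Safeguard (Protocol Section 5.1) | States a one-week contact? |
|---|---|
| Notice to provider or PCP; notice to clinic director | No interval for participant contact |
| Clinician assessment and JNC 8 triage | No interval stated in the documents |
| Medication review above 140/90 (component 3) | Takes place at each contact, so depends on when that falls |
| Recommended up-titration (component 3) | Every 2-4 weeks |
| Calls for poor BP control (component 4) | Every 2 weeks |
| Repeat chemistry panel (Adequacy of Protection, item d) | 7-10 days, only after an ACE inhibitor, ARB, diuretic or aldosterone antagonist is prescribed |

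**The case against.** The strongest reply is that this is a one-word slip whose intent is plain. The sentence follows the symptomatic rule and picks up the same alerts in people without symptoms, so a sensible reader would apply either limit. The slip is indeed the likely explanation, but staff at four sites act on the text, and the text gives two different triggers for the same reading.

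Second, the loss is limited. Medication change under this step is discretionary in any case. The same item says elsewhere, without the joint threshold, that intervention participants may have their regimen adjusted for high or low values. A participant at 190/95 is still assessed by a clinician, and the provider is still told. This stands: first clinical attention is not lost. What may be lost is the alert-specific medication step and the later study-staff contact.

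Third, the one-week sentence has no trigger of its own, so tying it to the preceding rule is an inference. On that same reading, control participants have no one-week contact even when both limits are crossed, so it is not a safety floor for the whole trial. Both points are fair. Reading the sentences in order is nonetheless the natural reading, and no other provision states this contact.

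Fourth, the counts depend on assumed diastolic inputs. That stands too. At SBP mean 138, the count is 2.8-4.7 visits if mean DBP is 80 and 9.4-20.0 if it is 90. Using 145 assumes no fall in SBP at all, and the eligibility criteria (Section 5.4) admit treated participants with no minimum BP, so the true mean may be lower. The counts also include any symptomatic participants, whom this sentence excludes. They indicate scale only; the contradiction does not depend on them.

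**Conclusion.** The concern holds. As written, the asymptomatic intervention-arm step contradicts the protocol's own alert definition and omits high alerts that cross one limit only. On the assumed diastolic range these are at least four in five high alerts (81-98%), or roughly 3 to 23 of 405 follow-up visits. Home averages would add to that by an amount the documents do not allow one to estimate.

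The practical gap is narrow: the alert-triggered medication step and, read in sequence, the one-week contact. Sample size, power, type I error and the primary analysis are untouched. It should still be corrected, because it is a wrong threshold in a safety rule that staff are expected to follow.

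**What to change.** In Protocol Section 5.1, Adequacy of Protection Against Risks, item b (Blood Pressure), in the sentence on intervention participants without acute symptoms, replace the 'and' between SBP >180 and DBP >110 with 'and/or'. That matches the alert definition and the symptomatic rule before it. Nothing else needs to change.

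The cost is one word in a protocol amendment and a few more one-week contacts: about 3 to 23 from study visits over the trial under the assumptions above, plus those prompted by home averages.

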### **Potential Benefits of the Proposed Research to the Subject and Others**

Potential benefits for subjects may include improved lifestyle and lower blood pressure with

a consequent reduction in cardiovascular risk. In our previous experience, subjects in biobehavioral research studies have generally found participation to be a positive experience and they often feel good about helping provide information that has the potential to help others like them. Potential benefits to others include the possibility that this research will lead to the development of more efficient and effective clinical treatments for patients with cardiovascular disease, with the expectation that this would lead to consequent reduction in subsequent, cardiovascular complications and death.

